Primary Objective:	
 - To describe when urinary hormones (follicle stimulating hormone and luteinising hormone) start to raise and when they reach their peak among male preterm neonates born with a gestational age <32 weeks. - To investigate if there is a difference in hormone levels and their peak timing between extremely preterm babies (<28 weeks of gestational age) and very preterm babies (28-32 weeks of gestational age).
Secondary Objective:	
 - Identify a link between hormone levels and linear growth in the first months of life in preterm neonates. - Identify a link between hormone levels and the development of external genitalia (testicular volume and position, penile length). - Identify a link between hormone levels and short-term neurocognitive development.
Rationale:	The knowledge about the activation of the hypothalamic-pituitary-gonadal axis (HPG) in the first months of life is relatively recent. It is scientifically proven that in this period, called "minipuberty", there is the same activation that occurs during puberty. This is responsible for changes in terms of growth, pubertal development and neurobehavioral patterns. Understanding all the factors involved in children's physical and neurocognitive development has a significant scientific impact and could provide useful information in case of future problems. As prematurity survival rates continue to improve, clinicians need to be familiar with the hormonal changes in these patients and the first months of life provide a 'window of opportunity' for functional studies of the HPG axis prior to pubertal development
Methodology:	This is a preliminary prospective and cross-sectional study.
Sample Size:	20 male preterm neonates with a gestational age ≤ 32 weeks
Main Inclusion Criteria:	
 • Male preterm infants born ≤ 32 weeks of gestational age • Written informed consent provided
Main Exclusion Criteria:	
 • Female sex assignment at birth • Male preterm infants born >32 weeks of gestational age • Male infants born at term

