A second post-natal HPG activation, also called "minipuberty", occurs at around 1 week of age, when placental hormones are cleared from the circulation. From the first weeks of life onwards there is a progressive increase in gonadotropins levels with a greater increase of FSH in females and of LH in males. During the "minipuberty" period gonadotropins levels have a peak at 3 months of life and a progressive exhaustion at around 6 months, except for FSH levels in females that can remain high even up to 3 or 4 years. Particularly in males, testosterone and androgen levels are associated with development and maturation of the reproductive system (penis and testis) as well as the androgynous cutaneous manifestations and a different neurobehavioral structure.⁵ Postnatal testosterone levels have been associated with male-type behaviour in 14-month-old infants, suggesting a role in neurobehavioral development.⁶ Recently, it has also been suggested how the increasing testosterone level during the first 6 months of life, as well as during puberty, translates into an increase of linear growth, regardless of the levels of growth hormone (GH) or insulin-like growth factor (IGF1).⁷ Preterm birth does not seem to influence post-natal HPG activation, since that gonadotropin levels seem to raise up at the same time as term infants after the birth. The difference is that in preterm neonates these values last higher and longer than full-term newborns. According to the most recent longitudinal data, the post-natal activity of this axis declines at about the same in term neonates compared to premature infants with the same corrected gestational age, suggesting that the HPG activity is evolutionarily regulated.^{8,9} This higher increase of gonadotropin levels in premature males has been associated with a faster penile and testicular growth after birth compared to full-term boys. At last, in neonates small for gestational age (SGA) there are some evidence that post-natal FSH and testosterone levels are higher compared to infants with an adequate weight (AGA), although it is not known

whether this correlates or have any influence on the catch-up growth of this subjects.^{10,11} Understanding how “minipuberty” can influence linear growth, genitalia development and neurocognitive processes in preterm neonates has a significant scientific impact and could provide us more information in understanding auxological and neurobehavioral developmental patterns of this population.

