2. Aim/Primary and Secondary Objectives

This is a preliminary prospective and crosssectional study aiming to describe “minipuberty” in male preterm children at the Royal Hospital for Children in Glasgow. The research project has been discussed by the Developmental Endocrinology Research Group at the University of Glasgow.

- **Primary Endpoint**

- To describe when urinary hormones (follicle stimulating hormone and luteinising hormone) start to raise and when they reach their peak among male preterm neonates born with a gestational age <32 weeks.
- To investigate if there is a difference in hormone levels and their peak timing between extremely preterm babies (<28 weeks of gestational age) and very preterm babies (28-32 weeks of gestational age).

- **Secondary endpoints**

- Identify a link between hormone levels and linear growth in the first months of life in preterm neonates.
- Identify a link between hormone levels and the development of external genitalia (testicular volume and position, penile length).
- Identify a link between hormone levels and short-term neurocognitive development.

3. Study Design

This is a preliminary prospective and cross-sectional study on male preterm children at the Royal Hospital for Children in Glasgow. The study will not include any investigational medical product. The research project has been discussed by the Developmental Endocrinology Research Group at the University of Glasgow.

This study will be performed according to the Research Governance Framework for Health and Community Care (Second edition, 2006).

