4.3 Laboratory Tests

Measurement of LH and FSH urinary levels will be made on fresh samples using electro-chemiluminescence immunoassay (ECLIA). Sample analysis will be performed by the Biochemistry Department of the Royal Hospital for Children in Glasgow using Abbott Architect i1600 instrument.

5. Assessment of Safety

We do not expect particular problems in this study. Urine collection will be made in the same way of routine collection in infants. Auxological evaluations are part of the routine care of preterm neonates and we will add a non-invasive evaluation of external genitalia without particular risks for the babies. Neurobehavioural development will be evaluated using parents' video only if they agree with video recording their baby. This will allow parents to stay at home without bringing their baby to the hospital.

6. Statistics and Data Analysis

Results shall be expressed as median (range) and analysed using Minitab. Some data may require log transformation. Pearson's correlation shall be used for univariate analysis of association of and multivariate analysis shall be performed using backward stepwise linear regression analysis including factors significant from univariate analysis (Pearson's correlation) as independent factors. The Mann Whitney U test shall be used for comparison of nonparametric data. Statistical significance shall be set at $p < 0.05$.

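### Gestational age enters a hormone–genitalia model only if it is significant in 20 infants, so a reported link may be partly confounded by degree of prematurity

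*Combined protocol and SAP*

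**What the plan says.** **Analysis.** Section 6, repeated in the synopsis, is the whole analysis plan. Pearson correlation is the univariate step, but the sentence does not say which variables are correlated: "Pearson's correlation shall be used for univariate analysis of association of and multivariate analysis". The multivariable step is "backward stepwise linear regression analysis including factors significant from univariate analysis". The only threshold given is p<0.05. No covariate is pre-specified, and gestational age does not appear in the section.

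**Sample size.** The synopsis gives "20 male preterm neonates with a gestational age ≤ 32 weeks", without an effect size, standard deviation or power.

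**Gestational age and hormone level.** The second primary objective (Section 2) is "To investigate if there is a difference in hormone levels and their peak timing between extremely preterm babies" and those born at 28–32 weeks. The Introduction says of gonadotropins that "in preterm neonates these values last higher and longer than full-term newborns". Section 4.1 uses cotton wool in the nappy for infants below 28 weeks and an adhesive bag for the others, so the measured hormone may differ by gestational age through collection alone.

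**Gestational age and genital outcomes.** The Introduction states: "This higher increase of gonadotropin levels in premature males has been associated with a faster penile and testicular growth after birth", compared with boys born at term. It also places completion of inguinoscrotal descent at about the 35th week. Testicular position, testicular volume and penile length are the genital outcomes (Section 4.2).

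**The concern.** Gestational age is fixed at birth, before any hormone is measured. If it is related to hormone level, and also to genital size or descent by a route other than the hormones, infants of different maturity will differ in both. Hormone and outcome will then correlate even if the hormone does nothing.

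The usual protection is to hold such a baseline variable constant because of what is known about it. Section 6 makes its inclusion depend on a significance test in 20 infants, which a real confounder of moderate strength can easily fail. Since gestational age is not listed as a candidate, the text also permits models in which it is never considered. At stake is whether a reported link for penile length, testicular volume or testicular position can be read as being about minipuberty rather than about how early the child was born.

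**Working it through.** The plan states no calculation to reproduce. From the documents: n = 20 and alpha = 0.05 (two-sided assumed). Everything else is an assumption: one standardised outcome and one hormone value per infant, no true hormone effect, correlation *a* between gestational age and hormone, and correlation *b* between gestational age and outcome. The documents give neither *a* nor *b*, so ranges are shown.

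**1. What the screen requires.** A factor passes if |r| ≥ t/√(n − 2 + t²). With t = 2.101 on 18 degrees of freedom, this is 2.101/√(18 + 4.414) = 0.444.

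**2. How often gestational age fails it.** By Fisher's z, power ≈ Φ(atanh(*b*)·√17 − 1.96). At *b* = 0.4: 0.424 × 4.123 = 1.747, and Φ(−0.213) = 0.42. Simulation with 200,000 cohorts per cell gives:

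| *b* | Gestational age fails the screen |
|---|---|
| 0.3 | 75% |
| 0.4 | 57% |
| 0.5 | 36% |
| 0.6 | 16% |

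**3. The spurious correlation.** With no hormone effect, the expected hormone–outcome correlation is *a* × *b*. It runs from 0.3 × 0.3 = 0.09 to 0.7 × 0.6 = 0.42.

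**4. How often a false link is reported** (same simulation; each range covers *b* = 0.3 to 0.6):

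| *a* | Pearson alone, or gestational age never offered | Screen plus backward elimination, gestational age offered | Gestational age forced in |
|---|---|---|---|
| 0.3 | 6.6–11.8% | 3.6–5.2% | about 5% |
| 0.5 | 9.6–25.4% | 5.4–6.8% | about 5% |
| 0.7 | 14.3–46.9% | 8.3–10.7% | about 5% |

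The first column covers both situations because a regression with the hormone as its only factor gives the same test as the Pearson correlation.

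**5. What forcing it in costs.** Variance inflation is 1/(1 − *a*²): 1/(1 − 0.25) = 1.33 at *a* = 0.5 and 1/(1 − 0.49) = 1.96 at *a* = 0.7. Now suppose that gestational age acts on the outcome only through the hormone, with a true hormone–outcome correlation of 0.5. Power then falls from about 61% under the plan's rule to about 51% at *a* = 0.5, and from about 57% to about 37% at *a* = 0.7.

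**The case against.** **The plan does not predict the confounding.** This stands. A reader might infer that the plan expects gestational age to drive hormone levels in this cohort. It asks whether levels differ. Its statement about higher levels compares preterm with term infants, and it also says that preterm birth does not seem to alter when activation occurs. The documents support gestational age as a possible determinant, no more.

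**The Introduction also fits a causal chain.** Prematurity may raise gonadotropins, which then speed genital growth. Under a pure chain the unadjusted link is not confounded, and adjustment only costs power, as step 5 shows. This stands as a reason for caution: the documents do not establish a common cause. They do not exclude a separate path either, and descent is described in terms of gestational weeks.

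**The large error rates do not belong to the stepwise rule.** This is also correct. It would be tempting to attach the figure of up to 47% to the screen. That figure applies to Pearson alone, or to models in which gestational age is never offered. If it is offered, inflation is absent at *a* = 0.3 and modest at 0.7. Nor does the screen always discard a moderate confounder more often than it keeps it; at *b* = 0.5 it keeps it in 64% of studies.

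**The movement model is an inference.** No text applies linear regression to Fidgety Movements, and no text links gestational age to movement at 3 months corrected age. The objective "Identify a link between hormone levels and short-term neurocognitive development" is therefore only plausibly affected.

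**The simulation simplifies the design.** It uses one value per infant, while Section 4 plans repeated urine samples and examinations. The percentages are illustrative.

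**Conclusion.** The point holds for the genital outcomes. Section 6 has no provision that ensures adjustment for gestational age, although the protocol's own text gives reasons to consider it on both the hormone and the outcome side. A reported link may be partly confounded. With no hormone effect and *b* between 0.3 and 0.6, the false-link rate runs from about 7–12% (*a* = 0.3) to 14–47% (*a* = 0.7) if gestational age is left out. If it is offered to the stepwise rule, the rate runs from about 5% to 8–11%. Forcing it in gives 5% throughout. All of this rests on assumed correlations and one value per infant.

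A reader might go further and conclude that two of the three secondary objectives cannot be interpreted. The documents do not support that: the case for Fidgety Movements rests on plausibility, and for the genital outcomes the confounding is possible and partial rather than demonstrated. That the study is preliminary does not remove the point, since it sets out to identify links and foresees publication.

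**What to change.** State in Section 6 that, for penile length, testicular volume and testicular position, the result answering the objective is the hormone association adjusted for gestational age at birth. Enter gestational age as a continuous variable, forced into the model whatever its univariate p-value. Report Pearson correlations as unadjusted and descriptive. Say which hormone value and which visit each model uses, because the adjustment cannot be applied without that.

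Apply the same adjustment to Fidgety Movements where the number of usable videos allows, noting that this model is inferred and the confounding there only plausible. One workable form makes log hormone the response, with movement class and gestational age as predictors.

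No new data are needed, since gestational age is already required for eligibility and grouping. The cost is one degree of freedom and lower precision: variance inflation of about 1.3–2.0 if gestational age and hormone correlate 0.5–0.7, which can take about 10–20 percentage points of power at n = 20. Estimates should therefore carry confidence intervals and be described as exploratory. A continuous term may not fully remove the change in urine collection at 28 weeks, and this should be stated as a limitation.

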7. STUDY CLOSURE / DEFINITION OF END OF TRIAL

Planned start date: February 2019

Planned end date: August 2020

Total duration: 18 months

The enrolment is expected to last 6 months starting from the approval.

The study will be finished at the last visit (12 months of corrected gestational age) of the last newborn enrolled.

8. Ethical Consideration

The study will be carried out in accordance with the World Medical Association Declaration of Helsinki (1964) and its revisions (Tokyo [1975], Venice [1983], Hong Kong [1989], South Africa [1996] and Edinburgh [2000]).

Favourable ethical opinion will be sought from an appropriate REC before patients are entered into this clinical trial. Patients will only be allowed to enter the study once their

parents have provided written informed consent. The CI will be responsible for updating the Ethics committee of any new information related to the study.

9. Finance and Indemnity

This study is sponsored by NHS Greater Glasgow & Clyde. The sponsor will be liable for negligent harm caused by the design of the trial. NHS indemnity is provided under the Clinical Negligence and Other Risks Indemnity Scheme (CNORIS).

11. Publications

We may report and disseminate the results of our study through peer reviewed scientific journals, internal report and conference presentation.

12. References

